6.5 Handling of Dropouts and Missing Data

With the exception of AE dates, missing data will not be imputed.

AE dates will be imputed for the purpose of calculating duration of events and treatmentemergent status (see Appendix A for imputation details and Appendix B for treatmentemergent definition). Censoring for time-to-event endpoints will be described in Section 7.5. with each planned analysis, as applicable.

Patients whose disease response cannot be assessed will be scored as non-responders for calculating the CR rate and ORR. Patients with missing values of a variable other than response endpoints (CR and ORR) and time-to-event endpoints (PFS and OS) will be excluded from the analysis of that endpoint unless otherwise specified.

6.6 Multicenter Studies

There are multiple sites in this study; however it is not anticipated that any one site will accrue enough patients to warrant an analysis by site.

6.7 Multiple Comparison/Multiplicity

No multiple comparisons are planned and no alpha adjustment is needed as there is only a single planned hypothesis test of the primary efficacy endpoint.

6.8 Examination of Subgroups

As exploratory analyses, subgroup analyses may be conducted for selected summaries. Subgroups may include but are not limited to the following:

- Age (18-64 years, \geq 65 years old)
- Gender (Male, Female)
- Categorized weight at baseline(<70, 70-99 and >=100 kg)

• Baseline ECOG performance status (0, 1, 2)

6.9 Covariates

Adjustment for covariates will not take place for analysis of the primary efficacy endpoint of CR rate. Subgroup analyses and covariate adjusted analyses may be carried out for particular covariates of interest. Exploratory analysis of biomarker and pharmacodynamic endpoints may also incorporate covariate adjustment.

6.10 Timing of Analyses

The trial is not designed to allow for early stopping for futility or favorable efficacy results.

Analysis including hypothesis test of the CR rate for the primary endpoint for parts 1 and 2 will be carried out after all patients have had their final response assessment prior to proceeding to ASCT, starting a new anti-cancer therapy, or discontinuing from the study.

Interim summaries of various endpoints may be presented at scientific congresses prior to the final analysis of the primary endpoint. Interim summaries will also be presented to the SMC.

7 PLANNED ANALYSES

7.1 Disposition

An accounting of study patients by disposition will be tabulated overall and by dose regimen

- The number of patients in each analysis set will be summarized.
- The number and percentage of patients who discontinued treatment will be summarized by the primary reason for treatment discontinuation.
- The number and percentage of patients who discontinued the study will be summarized by the primary reason for study discontinuation.
- The number and percentage of screened patients who subsequently enrolled will be summarized.
- Follow up time and subsequent treatment information will be summarized.
- The number of screen failures will be summarized overall and by primary reason for screen failure.

Listings of disposition data will be presented by patient for all enrolled patients, including the primary reasons for end of treatment and end of study for each subject.

7.2 Demographic and Baseline Characteristics

Demographics and baseline characteristics will be presented as listings and in tabular form overall and by dose regimen using the all enrolled patients analysis set. Demographics and baseline characteristics include age, gender, ethnicity, race, height, and weight.

The following disease specific characteristics will be summarized with respect to initial diagnosis and baseline status (as appropriate):

- initial disease diagnosis
- time from initial diagnosis to first dose of study drug
- time from relapse to first dose of study drug
- number and type of prior therapies
- response to prior lines of therapy
- disease stage
- bulky disease status
- extranodal disease status
- bone marrow disease involvement
- B symptoms
- current disease status relative to fronline treatment.

7.3 Protocol Deviations

Important protocol deviations (defined as protocol violations by Seattle Genetics) are those that represent a divergence from the protocol that could have a significant effect on the integrity of the study data, or on the subject's rights, safety, or welfare. Important protocol deviations also include exemptions to the study inclusion/exclusion criteria and will be summarized by category for the All Enrolled Patients analysis set. A list of patients with important protocol deviations will be presented.

7.4 Treatment Administration

Treatment administration will be summarized overall and for each dosing schedule using the All Treated Patients analysis set. Summary statistics for duration of therapy (weeks) and the number of cycles per patient will be presented, as well as the number and percentage of patients who were treated at each cycle and completed each cycle. Cumulative dose (mg), absolute dose intensity (ADI) and relative dose intensity (RDI) will be described. The number and percentage of patients whose dose was ever modified will be summarized by modification type, cycle and overall (i.e. overall drug administrations for a patient); listings may be presented as well. Dose modifications by dose may also be presented.

Duration of treatment (except when calculating exposure) is defined as the time from first dose date of any infusional component of study treatment to the earliest of either:

- 1. last dose date of any infusional component of study treatment + 21, or;
- 2. date of death

For the purpose of calculating exposure summaries, duration of treatment is defined as time from the first dose to 21 days after the last dose [(last dose date+21)–first dose date].

Intended Dose Intensity (IDI) is defined as the intended dose of drug (e.g. 1.8 mg/kg) per unit of time. Intended dose is based on the dose which was intended to be administered at the

start of the planned treatment regimen (thus a dose reduction or elimination is not considered planned, even though it may be indicated per protocol due to, e.g., occurrence of AEs). If a patient discontinues treatment for a reason unrelated to AEs, such as progressive disease, then the subsequent doses are not considered as intended for the purpose of calculating dose intensity. The IDI for brentuximab vedotin and nivolumab at possible dose regimens is presented in the following table:

		Unit of time per cycle	
Regimen Component	Intended Dose Regimen	(weeks)	IDI
brentuximab vedotin	1.8 mg/kg	3	0.60
brentuximab vedotin	1.2 mg/kg	3	0.40
nivolumab	3 mg/kg	3	1.00
nivolumab	1 mg/kg	3	0.33

Absolute Dose Intensity (ADI) is defined as the actual dose (e.g. 1.8 mg/kg) per unit of time that the patient received over the entire treatment period.

Relative dose intensity (RDI) is defined as the absolute dose intensity over the intended dose intensity.

$$RDI = ADI/IDI * 100.$$

Example dose intensity calculation

For brentuximab vedotin, consider a patient treated with an intended dose regimen of 1.8 mg/kg for four cycles. The second dose was delayed for one week, and for the third cycle of the infusion was not completed and the patient received less than the full dose. At the fourth cycle the dose is not given at all due to an AE.

Visit	Intended Dose Regimen (mg/kg)	Intended Dose (mg)	Actual Dose (mg)	Cycle Length
C1D1	1.8	38	38	3 weeks + 1 week delay
C2D1	1.8	38	38	3 weeks
C3D1	1.8	38	19	3 weeks
C4D1	1.8	38	0	3 weeks

ADI (per week):

=
$$(1.8 + 1.8 + (1.8*[19/38]) + 0) / (3 \text{ wks} + 1 \text{ wk delay} + 3 \text{ wks} + 3 \text{ wks} + 3 \text{ wks})$$

mg/kg per week
=0.35 mg/kg per week

one mg ng per wee

RDI:

7.5 Efficacy Analyses

The test of the primary efficacy endpoint of CR rate will be carried out using the All Enrolled Patients analysis set. Other efficacy analyses will be carried out using the All Enrolled Patients analysis set, and may also be presented using the Efficacy Evaluable analysis set or the All Treated Patients analysis set.

Unless otherwise specified, efficacy analyses will be presented by dose regimen and overall.

Additional exploratory subgroup analyses may be carried out as well.

7.5.1 Primary Efficacy Endpoints

7.5.1.1 Complete Remission (CR) Rate

CR rate is defined as the proportion of patients with best response of CR prior to ASCT or initiation of subsequent antitumor treatment not specified in the protocol. Response is by investigator assessment according to the Lugano Classification Revised Staging System for malignant lymphoma (Cheson 2014). For Part 3, the response assessment will also incorporate the Lymphoma Response to Immunomodulatory Therapy Criteria (LYRIC) (Cheson 2016). Patients whose response to treatment cannot be adequately assessed according to the specified criteria will be classified as non-responders for the purpose of calculating CR rate.

The primary efficacy hypotheses can be expressed as follows:

 H_0 : CR Rate for brentuximab vedotin + nivolumab is $\leq 30\%$

H_A: CR Rate for brentuximab vedotin + nivolumab is >30%

The CR rate at EOT will be calculated using the All Enrolled Patients analysis set and will include all patients in this analysis set who were enrolled at the dose regimen chosen for Part 2. The test of the primary hypothesis will be carried out using a one-sided exact binomial test at level $\alpha = 0.05$, thus the null will be rejected in favor of the alternative if p <0.05 is observed. CR rate and its two-sided 90% (to correspond with the level of the test) exact binomial confidence interval will be calculated (Clopper 1934). Additionally, the two-sided 95% exact binomial confidence interval will be presented as a descriptive summary.

CR rate will also be summarized separately for patients enrolled under dose regimens other than that chosen for part 2 of the study. Overall summaries of CR rate may be presented as well. These summaries will be considered exploratory in nature.

7.5.2 Secondary Efficacy Endpoints

7.5.2.1 Objective Response Rate (ORR)

ORR is defined as the proportion of patients with best response of CR or PR prior to ASCT or initiation of subsequent antitumor treatment not specified in the protocol. Response is by investigator assessment according to the Lugano Classification Revised Staging System for malignant lymphoma (Cheson 2014). Patients whose response to treatment cannot be

adequately assessed according to the specified criteria will be classified as non-responders for the purpose of calculating ORR.

The ORR at EOT will be calculated using the All Enrolled Patients set and its two-sided 95% exact binomial confidence interval will be presented (Clopper 1934). ORR will be presented by dose regimen and overall. Additional summaries of ORR may be presented based on patient demographics of interest. Summaries may also be presented using the All Treated Patients and the Efficacy Evaluable analysis sets.

7.5.2.2 Progression-Free Survival (PFS) after ASCT

PFS after ASCT is defined as the time from ASCT to the first documentation of PD or to death due to any cause, whichever comes first. Patients who do not undergo ASCT or receive additional anti-cancer therapy (such as an alternate salvage regimen) prior to ASCT will not be included in the analysis of this endpoint. Date of ASCT is defined as the reported date of stem cell infusion for ASCT. Documentation of PD should be consistent with the criteria described in section 6.4. Specifically, PFS after ASCT will be calculated as:

PFS after ASCT = Date of first documented PD or death – Date of ASCT + 1.

PFS data will be censored as follows:

- Patients who do not have tumor progression and are still on study at the time of an analysis will be censored at the date of the most recent disease assessment prior to the analysis which was adequate to document progressive disease
- Patients who have started an antitumor treatment (excluding high-dose conditioning regimens pre-ASCT, consolidative radiotherapy pre- or post-ASCT, or consolidative treatment with single-agent brentuximab vedotin post-ASCT) other than the study treatment prior to documented PD will be censored at the date of the most recent disease assessment which was adequate to document PD prior to start of new therapy
- Patients who are removed from study prior to documentation of tumor progression
 will be censored at the date of the most recent disease assessment prior to study
 discontinuation which was adequate to document disease progression

If a patient does not have any adequate disease assessments after ASCT their PFS will be censored at one day.

Kaplan-Meier Curves depicting PFS will be generated. Additionally, median PFS and probability of PFS from 3 months to the end of the follow-up period will be reported at 3 month intervals. The two-sided 95% confidence intervals (CI) for the median and 3-month intervals will be calculated using the complementary log-log transformation method (Collett 1994).

Exploratory subgroup analyses may be carried out; these analyses may involve different definitions of events and/or different censoring rules.

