## 6.7 Long-term Follow-up ( $\pm 2$ weeks)

Patients who discontinue from both study drugs (brentuximab vedotin and nivolumab) will remain on the study for follow-up until withdrawal of consent, death, or study closure,

whichever occurs first. Long-term follow-up assessments will be performed at the following time points post-ASCT (or post-EOT for patients who do not undergo ASCT): 100 days and then 6, 9, 12, 18, 24, 30, and 36 months and then per institutional standard thereafter.

Patients who have discontinued treatment due to PD or who have initiated subsequent systemic chemotherapy will not have response assessed but will be followed for survival. Patients will be followed at this schedule until withdrawal of consent, death, or study closure, whichever occurs first. The following assessments will be performed until disease progression; patients will be followed for survival thereafter.

- Dedicated CT of chest, neck, abdomen, and pelvis; performed at 100 days and then 6, 12, 24, and 36 months post-ASCT or post-EOT long-term follow-up visits or if progression is suspected based on clinical signs and symptoms
- PET; performed with CT scans until the patient achieves a complete metabolic response (CmR) by PET
- Interval medical history to assess changes in health status since prior visit
- Physical examination
- Disease progression status and post-study treatment received

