### 9.2.2.2 Progression-Free Survival (PFS) after ASCT

PFS after ASCT is defined as the time from ASCT to the first documentation of PD or to death due to any cause, whichever comes first. Patients who do not undergo ASCT will not be included in the analysis of this endpoint. Documentation of PD must be consistent with the criteria described in Section [7.2](#). Specifically, PFS will be calculated as:

$$\text{PFS} = \text{Date of first documented PD or death} - \text{Date of ASCT} + 1.$$

PFS data will be censored as described below:

- Patients who do not have PD and are still on study at the time of an analysis will be censored at the date of the most recent disease assessment prior to the analysis which was adequate to document PD
- Patients who have started an antitumor treatment (excluding high-dose conditioning regimens pre-ASCT, consolidative radiotherapy pre- or post-ASCT, or consolidative treatment with single-agent brentuximab vedotin post-ASCT) other than the study treatment prior to documented PD will be censored at the date of the most recent disease assessment which was adequate to document PD prior to start of new therapy
- Patients who are removed from study prior to documentation of PD will be censored at the date of the most recent disease assessment prior to study discontinuation which was adequate to document PD.

If a patient does not have any adequate disease assessments after ASCT their PFS will be censored at one day.

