9 CHANGES FROM PLANNED ANALYSES

9.1 Changes from the Original Protocol

There are no changes from the original protocol.

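### SAP 7.5.2.2 narrows the population for PFS after ASCT without declaring it, and neither document ties progression to the period after transplant

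*SAP*

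**What the plan says.** **Population.** Protocol 9.2.2.2 has one exclusion: "Patients who do not undergo ASCT will not be included in the analysis of this endpoint". SAP 7.5.2.2 has two: "Patients who do not undergo ASCT or receive additional anti-cancer therapy (such as an alternate salvage regimen) prior to ASCT will not be included". SAP 9.1 then states: "There are no changes from the original protocol".

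**Time.** In both documents the time is "Date of first documented PD or death" minus the date of ASCT, plus one day. The SAP adds that the date of ASCT is the date of stem cell infusion.

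**New therapy.** In protocol 9.2.2.2, a patient who starts other antitumor treatment before documented progression "will be censored at the date of the most recent disease assessment which was adequate to document PD prior to start of new therapy". The rule exempts some treatments, "excluding high-dose conditioning regimens pre-ASCT, consolidative radiotherapy pre- or post-ASCT" among them. The SAP repeats both the rule and its exemptions.

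**Backstop.** Both documents have the same default: "If a patient does not have any adequate disease assessments after ASCT their PFS will be censored at one day".

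**Data collection.** Protocol 6.7 covers patients who stopped treatment for progression and those "who have initiated subsequent systemic chemotherapy will not have response assessed but will be followed for survival".

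**Which text governs.** Protocol 9.3 calls its own analysis text a summary of the fuller SAP. It requires a protocol amendment for a change of method only where site conduct is affected.

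**The concern.** A patient who needs another salvage regimen between the study combination and transplant is, in most cases, one whose response did not lead straight to ASCT. Whether such patients are counted changes the question the endpoint answers: the outcome of everyone transplanted, or the outcome of those who went from the combination to transplant with nothing in between. Both are legitimate descriptive questions, but they are different ones. A reader who has the protocol definition and the statement in SAP 9.1 would assume the first and be given the second.

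The study is open-label. This SAP covers Part 3, so its text postdates the interim response results in protocol 3.2.1. The documents do not show when the exclusion was introduced. That is a reason to declare it; it is not evidence that data drove it.

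The time origin is a separate matter. A rule written for a clock that starts at enrollment has been applied to one that starts at transplant, and nothing requires the end date to come after the start date.

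**Working it through.** No sample size, event count or power is stated for this endpoint, so there is no plan figure to reproduce.

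**1. Is the population change declared anywhere?** The protocol population is all transplanted patients. The SAP population is all transplanted patients less those given other therapy first. The protocol's amendment history lists no change to the population in 9.2.2.2, and SAP 9.1 lists none. The difference is real and unrecorded.

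**2. What time do the rules give when progression or new therapy precedes ASCT?** Take day 1 as Cycle 1 Day 1.
- Cycle 4 Day 1 = 1 + 3 × 21 = day 64.
- End-of-treatment scan, Parts 1 and 2 (23 to 37 days after last dose): days 87 to 101. Part 3 (15 to 30 days): days 79 to 94.
- Cycle 2 CT: 21 + 15 to 21 + 21, that is days 36 to 42.

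If G is the number of days from the relevant scan to ASCT, then time = scan date − (scan date + G) + 1 = 1 − G. The result does not depend on the scan day. G is not in the documents; these values are assumptions:
- G = 30: −29 days
- G = 60: −59 days
- G = 90: −89 days
- G = 180: −179 days

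Under the protocol this applies to censoring at the last scan before alternate salvage, and to progression before transplant (for progression at the Cycle 2 CT, G was taken as 60 to 180). Under the SAP the alternate-salvage patients are removed, so only the second route remains: progression on study followed by transplant with no other therapy. Protocol 3.1.1 and 3.1.2 set no minimum response for ASCT, so the documents do not rule this out.

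The one-day default limits this. A patient with no adequate assessment after ASCT is censored at +1 day. Protocol 6.7 plans no response assessment after treatment was stopped for progression or after subsequent systemic chemotherapy, so many such patients would fall there. The literal outcome is a negative time if an adequate post-ASCT assessment exists, and +1 day otherwise. Neither carries post-transplant information.

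**3. Which way does the exclusion move the estimate?** Inputs from the protocol: 18 of 29 complete responses and hence 11 of 29 without (3.2.1, interim); long-term relapse-free survival of about 75% with metabolic complete response before ASCT and about 25% with residual disease (1.4). Assumptions: everyone is transplanted; switchers' outcome lies between 25% and 75%.
- Half of the non-complete responders switch. SAP population: (18 × 0.75 + 5.5 × 0.25) / 23.5 = 63.3%. All transplanted: (14.875 + 5.5 × 0.25) / 29 = 56.0%, to (14.875 + 5.5 × 0.75) / 29 = 65.5%. Difference: +7.3 to −2.2 points.
- All of them switch. SAP population: 75%. All transplanted: (13.5 + 11 × 0.25) / 29 = 56.0%, to (13.5 + 11 × 0.75) / 29 = 75.0%. Difference: +19.0 to 0 points.

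The sign is not fixed, and the switching rate is unknown.

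**4. What counts as additional therapy in the SAP?** The SAP dates ASCT at infusion, so conditioning always comes before it. The new-therapy censoring bullet exempts conditioning and pre-ASCT consolidative radiotherapy; the exclusion sentence exempts neither. Read literally, it could remove every transplanted patient who received conditioning. The example it gives, alternate salvage, suggests this is not intended.

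**The case against.** The strongest reply is that the SAP is the governing text and improves on the protocol. Protocol 9.3 allows the SAP to refine methods without an amendment. The SAP states its exclusion openly in the endpoint definition, and that exclusion removes the negative-time problem for alternate-salvage patients. It also matches the way CR rate and ORR stop counting at subsequent antitumor treatment. PFS from enrollment and overall survival use all enrolled patients, and SAP 7.1 already summarizes subsequent treatment. The endpoint is descriptive, with no hypothesis test. All of this stands. It limits the weight of the point, but permission to change a method does not make a statement of no changes correct.

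Three stronger readings are tempting, and the documents do not support them:
- A reader might infer that the endpoint has no single valid population. The SAP defines one; what is missing is the declaration, a label, and a definition of additional therapy.
- A reader might infer that the exclusion flatters post-transplant PFS. The range in the working includes zero and negative values, and its upper end needs every non-complete responder to switch and to keep the residual-disease outcome after a further regimen. Patients in partial response or stable disease who go straight to transplant stay in, so the population is not restricted to responders.
- A reader might infer that the protocol gives every switcher a negative time. The one-day default prevents that wherever no adequate post-ASCT assessment exists.

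**Conclusion.** The point holds as a discrepancy and a drafting fault in a secondary descriptive endpoint. The population was narrowed on a criterion related to outcome, and SAP 9.1 says nothing changed. In both documents the progression date is not required to follow ASCT; in the protocol the new-therapy censoring date can precede it as well. The SAP exclusion conflicts, on its wording, with its own exemptions for conditioning and consolidative radiotherapy.

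The population mismatch and the rule faults rest on the text alone. The negative times of −29 to −179 days rest on assumed gaps of 30 to 180 days. The −2 to +19 point range rests on an interim response count, approximate historical relapse figures, universal transplant and assumed switching rates; it shows only that size and direction cannot be determined from the documents. No count or expected rate of alternate salvage before ASCT is given.

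A reader might also conclude that the post-transplant imaging in protocol 6.7 must be extended to switchers. That does not follow from a fault that SAP text can correct. It would alter site conduct and so need a protocol amendment, and Parts 1 and 2 had finished enrolling before Part 3 was added.

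**What to change.** Amend the SAP before database lock:

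- (a) List the population change in 9.1.
- (b) In 7.5.2.2, label the analysis as PFS after ASCT in patients transplanted without intervening therapy. State that conditioning and pre-ASCT consolidative radiotherapy are not additional therapy, to match the censoring bullet.
- (c) Report how many transplanted patients are excluded, with their end-of-treatment response.
- (d) State that only progression or death after stem cell infusion counts as an event, and that the new-therapy censoring rule applies only to therapy started after infusion.
- (e) Optionally, show all transplanted patients as a supportive analysis. Note that post-ASCT progression is not systematically collected for those followed for survival only under protocol 6.7, so this analysis would be limited.

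The cost is a few sentences of SAP text and a small table, plus one more Kaplan-Meier display if (e) is taken up. No new data collection is needed.
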